10.0 Efficacy Analysis**10.1 General Considerations**

All statistical tests will be two-sided with the significance level of 0.05. Descriptive statistics will be provided. These include the number of observations, mean, standard deviation, minimum, median, and maximum for continuous variables; and counts and percentages for discrete variables. The analysis will be performed using SAS® (SAS Institute Inc., Cary, NC, USA). All efficacy analysis will be performed using I-ITT-RP and J-ITT-RP analysis set for the Maintenance Study, unless otherwise specified.

10.2 Primary Efficacy Analysis

This section provides the details of the primary efficacy analysis for the Maintenance Study.

Primary Efficacy Variable:

The primary efficacy variable for the Maintenance Study is the proportion of Week 8 responders (per Full Mayo score) achieving clinical remission (per Full Mayo score) at Week 52.

Analysis Data Set for the Primary Efficacy Analysis:

The primary efficacy analysis will use the I-ITT-RP analysis set for the Maintenance Study.

Imputation Method used for the Primary Efficacy Analysis:

The primary efficacy analysis will use the NRI method to impute the missing values at Week 52 for the Maintenance Study. Subjects with missing primary endpoint data at Week 52 will be classified as "no clinical remission."

Statistical Method of the Primary Efficacy Analysis:

The primary analysis of the Maintenance Japan Sub-Study will compare the Week 8 responders (per Full Mayo Score) in the eow regimen versus the subjects in the ew regimen in the I-ITT-RP analysis set. The difference between the treatment regimens in the proportion of subjects achieving clinical remission at Week 52 will be assessed using Cochran-Mantel-Haenszel (CMH) test adjusted for Induction treatment regimen and remitter status at Week 8, where Week 8 remitter status will be determined based on the Full Mayo Score using the endoscopy subscore from the central reader. A CMH based two-sided 95% confidence interval for the difference between treatment groups will be calculated. Breslow-Day test for homogeneity of odds ratios will be performed as well.

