4.0 Study Objectives, Design and Procedures

4.1 Objectives

The Japan Sub-Study objective is to evaluate the safety and efficacy of higher induction and maintenance dosing regimens in subjects with moderately to severely active ulcerative colitis and to show the consistency of efficacy between Japanese population and integrated population of Japanese and Western subjects from the Main Study.

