4.3 Sample Size

One hundred Japanese subjects have been determined as the proper sample size for the Japan Sub-Study based on the following rationale. Using the same assumptions as the Main Study with the following:

- Remission rate for induction treatment at 8 weeks: 35% in the high dose group and 20% in the standard dose group
- Remission rate for maintenance treatment at 52 weeks among Week 8 responders: 48% in the high dose group and 30% in the standard dose group
- Overall response rate for induction treatment at Week 8: 50%
- $\alpha = 5\%$, power = 95% for induction study
- $\alpha = 5\%$, power = 90% for maintenance study

The precisions of point estimations of remission rates in Japanese population are included within the 95% CI of remission rates in integrated population will be within 20% with 100 subjects. With this sample size, the probability to show consistency between Japanese population and integrated population will be greater than 80% using the method 2 shown in the "Basic principles on global clinical trials."

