5.0 Analysis Populations

5.1 Definition for Analysis Populations

The Japanese population is defined as all Japanese subjects who were randomized at sites in Japan. The following populations will be used for analyses in Japan Sub-Study:

Integrated Intent-to-Treat maintenance (I-ITT) population includes all subjects who are re-randomized at both Japanese sites and all other sites in the Main Study at Week 8 into the Maintenance Study. The Japan ITT (J-ITT) dataset includes all Japanese subjects who are re-randomized at Japanese sites at Week 8 into the Maintenance Study. I-ITT and J-ITT subjects will be analyzed as randomized.

Integrated ITT-Responder (I-ITT-RP) population includes all subjects in I-ITT who achieve Week 8 response based on the Full Mayo Score utilizing the endoscopy subscore provided by the central reader. Japan ITT-Responder (J-ITT-RP) population includes all subjects in J-ITT who achieve Week 8 response based on the Full Mayo Score utilizing the endoscopy subscore provided by the central reader. I-ITT-RP and J-ITT-RP are the populations for the efficacy analysis of Week 8 responders during the Maintenance Study.

Integrated ITT-Non-Responder (I-ITT-NRP) population includes all subjects in I-ITT who do not achieve Week 8 response based on the Full Mayo Score utilizing the endoscopy subscore provided by the central reader. Japan ITT-Non-Responder (J-ITT-NRP) population includes all subjects in J-ITT who do not achieve Week 8 response based on the Full Mayo Score utilizing the endoscopy subscore provided by the central reader. ITT-NRP is the population for the efficacy analysis of Week 8 non-responders during the Maintenance Study.

Integrated ITT-Remitter (I-ITT-RM) population includes all subjects in I-ITT who achieve Week 8 remission based on the Full Mayo Score utilizing the endoscopy subscore provided by the central reader. Japan ITT-Remitter (J-ITT-RM) population includes all subjects in J-ITT who achieve Week 8 remission based on the Full Mayo Score utilizing

the endoscopy subscore provided by the central reader. I-ITT-RM and J- ITT-RM is the population for the efficacy analysis of Week 8 remitters during the Maintenance Study.

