10.6 Efficacy Subgroup Analysis

The subgroups listed below will be used in subgroup analyses of the primary endpoint of the Maintenance Study.

- Sex (male, female)
- Age (\leq median, $>$ median)
- Race (white, non-white)
- Baseline corticosteroid use (yes, no)

- Baseline immunosuppressant use (yes, no)
- Baseline Mayo Score (≤ 9 , > 9)
- Baseline Mayo Score (\leq median, $>$ median)
- Prior exposure to anti-TNF (yes, no)
- Baseline weight (\leq median, $>$ median)
- Presence of pancolitis at Baseline (yes, no)
- Disease duration at Baseline (\leq median, $>$ median)
- Baseline hs-CRP (≤ 5 mg/L and > 5 mg/L)
- Baseline hs-CRP (\leq median, $>$ median)
- Baseline albumin (\leq median, $>$ median)
- Region (US versus non-US)

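### Maintenance SAP 3.0 excludes the Main Study data on which the 10.2 primary analysis is built, and 10.2 states no overall Japanese estimate for the primary endpoint

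*SAP*

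**What the plan says.** All references are to the Maintenance SAP unless the Induction SAP is named.

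- **Aim.** Section 4.1 sets out "to show the consistency of efficacy between Japanese population and integrated population of Japanese and Western subjects from the Main Study". Section 4.3 justifies the 100 Japanese subjects on the same ground: "the probability to show consistency between Japanese population and integrated population will be greater than 80% using the method 2".
- **Sets.** In 5.1 the integrated population "includes all subjects who are re-randomized at both Japanese sites and all other sites in the Main Study at Week 8". I-ITT-RP is its Week 8 responder subset and J-ITT-RP is the Japanese counterpart. Section 5.1 adds: "I-ITT-RP and J-ITT-RP are the populations for the efficacy analysis of Week 8 responders during the Maintenance Study".
- **Default.** Section 10.1: "All efficacy analysis will be performed using I-ITT-RP and J-ITT-RP analysis set for the Maintenance Study, unless otherwise specified".
- **Primary endpoint.** Section 10.2: "The primary efficacy analysis will use the I-ITT-RP analysis set for the Maintenance Study". Its method paragraph repeats the choice, comparing eow responders "versus the subjects in the ew regimen in the I-ITT-RP analysis set".
- **Exclusion.** Section 3.0 says that data from anyone enrolled under the Main Study are left out of the analyses this SAP describes, and that the Main Study will have its own SAP.
- **Region.** The only geographic subgroup of the primary endpoint in 10.6 is US against non-US.
- **Induction SAP.** Its 10.2 names both I-ITT and J-ITT for the primary endpoint.

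**The concern.** Two separate problems bear on the same objective.

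First, 3.0 and 10.2 cannot both be followed. A set that contains Main Study subjects by definition cannot be analysed under a rule that removes them. Removing them would also take away the integrated comparator that 4.1 needs.

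Second, a consistency assessment needs the ew-minus-eow difference in Japan beside the difference in the integrated set. For the primary endpoint, 10.2 states only the second. Whether and how the overall Japanese result is shown is then left to be decided later, for the endpoint where consistency matters most.

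**Working it through.** **1. The plan's own figures (4.3).** Inputs: 100 Japanese subjects, 50% Week 8 response, 1:1 re-randomization (4.2), Week 52 remission 48% against 30%. Japanese responders per arm: 100 × 0.50 / 2 = 25.

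- Precision of a Japanese rate, 1.96 × √(p(1−p)/25): 19.6 points at 48% and 18.0 points at 30%. Both are within the stated 20%.
- Consistency probability. The SAP does not spell out method 2. If it is assumed to ask that the Japanese difference point the same way as the integrated one, then with v = 0.48×0.52 + 0.30×0.70 = 0.4596, Φ(0.18 / √(v/25)) = Φ(0.18/0.1356) = 90.8%. Exact binomial gives 88.1%, or 92.9% counting ties. The same reading gives 95.5% for induction and 0.955 × 0.908 = 86.7% for both together. The stated figure above 80% reproduces on that assumption. If at least half of the assumed effect had to be retained, the maintenance figure would be 74.7%.

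Both of these readings take the Japanese treatment difference as input, and 10.2 does not state that quantity.

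**2. The rules side by side.**

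| Section | Main Study data | Set for Week 8 responders |
|---|---|---|
| 3.0 | excluded | – |
| 5.1 | included in I-ITT and I-ITT-RP | I-ITT-RP and J-ITT-RP |
| 10.1 | included through I-ITT-RP | both, with an exception clause |
| 10.2 | included through I-ITT-RP | I-ITT-RP only |
| Induction SAP 10.2 | included through I-ITT | I-ITT and J-ITT (all randomized subjects) |

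Following 3.0 loses the integrated comparator. Following 10.2 alone loses the overall Japanese estimate.

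**3. Can the pooled result supply the Japanese answer?** Main Study responders per ew or eow arm: 840 × 0.50 × 2/5 = 168, using the 2:2:1 ratio in Induction SAP 4.2. The Japanese share is 25 / (25 + 168) = 25/193 = 13%.

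- Japan matches the Main Study: expected pooled difference 18.0 points.
- Japan has no effect: 18.0 × 168/193 = 15.7 points.

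If the response rate is 40% or 60% in both populations the share stays at 13% (20/154, 30/232). If the rates differ, 40% in Japan with 60% in the Main Study gives 18.0 × 202/222 = 16.4 points, and the reverse gives 18.0 × 134/164 = 14.7 points.

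The pooled test is similarly insensitive. Treated as a single table, it rejects about 96% of the time if Japan matches and about 89% if Japan has no effect (39% in both arms).

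**4. Precision of the missing estimate.** The 95% CI half-width is 1.96 × √(v/n).

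- J-ITT-RP: 26.6 points at n = 25, 29.7 at n = 20, 24.3 at n = 30.
- I-ITT-RP: 9.6 points at n = 193.

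**The case against.** **Section 10.2 as a permitted exception.** A reader might infer that 10.2 contradicts 10.1. It does not: the default in 10.1 gives way where something else is specified, and 10.2 specifies it. Section 10.2 can also be read as naming only the set for the confirmatory test that opens the fixed sequence in 10.5. This stands. What remains is that 10.2 does not say so, that 5.1 carries no such exception, and that the exception falls on the primary endpoint.

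**Japanese results are not wholly absent.** A reader might infer that the plan has no Japanese efficacy results. The 10.1 default still covers J-ITT-RP for secondary endpoints in responders. Section 10.6 names no set, so the default arguably gives J-ITT-RP subgroup tables of the primary endpoint. This stands too. The gap is the overall J-ITT-RP line.

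**Section 3.0 will not be applied literally.** A reader might infer that the primary comparison would shrink to 25 responders per arm, with power of about 28%. The rest of the SAP does not support that outcome. Sections 5.1, 7.1, 8.0, 10.1, 10.2 and 11.1 all use integrated sets, and 4.4 times the final analysis by the last I-ITT subject. The likely intent was to keep out Main-Study-only analyses. The sentence is still wrong as written.

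**The dilution figure holds for any pooled test.** This is true, and the SAP nowhere says that the pooled test shows consistency. The figure shows only that the stated primary result cannot replace a Japanese estimate.

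**Region.** A Japan level in 10.6 is not needed once both sets stand in 10.2. In the Induction SAP, Japan is a region level only as a covariate in a sensitivity model, and that plan's subgroup list has no region. This limb is optional.

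**Conclusion.** The point holds in two parts. Section 3.0 contradicts 5.1 and 10.2 on Main Study data. Section 10.2, though allowed by 10.1, leaves the overall Japanese estimate of the primary endpoint unstated, against the objective in 4.1, the sizing in 4.3, the populations in 5.1 and the practice of the Induction SAP.

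The pooled result cannot fill the gap: Japan is about 13% of it, and no Japanese effect moves the expected difference by 18.0 − 15.7 = 2.3 points. This rests on the 4.3 rates, equal response in both populations and the 2:2:1 Main Study ratio. With unequal response of 40% and 60% the shift is 1.6 to 3.3 points.

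The confirmatory test on I-ITT-RP is sound and unaffected. This is a matter of making the plan serve its stated objective, and it should be settled before the results are known.

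**What to change.** 1. **Section 3.0.** Reword the exclusion so that it covers Main-Study-only analyses and does not reach the integrated sets.
2. **Section 10.2.** Keep I-ITT-RP for the primary test and add J-ITT-RP as an estimate. Report the ew-minus-eow difference with its 95% CI in both sets, side by side, as the input to the consistency assessment that 4.3 already cites. State that the J-ITT-RP result lies outside the fixed-sequence testing of 10.5.
3. **Optional, Section 10.6.** Add a Japan level to the region subgroup for I-ITT-RP. Region is constant in J-ITT-RP and gives nothing there.

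Cost: a few sentences and one extra column in the primary table, with no new data and no change to the primary test or alpha. The drawback is precision. With a half-width of about 27 points (24 to 30 for 30 to 20 responders per arm), the Japanese interval will probably include zero even if the assumed 18-point effect is real, so it should be read as an estimate and not as a test.

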10.3 Secondary Efficacy Analyses

For the analysis purpose, the secondary efficacy endpoints are divided into two groups: (1) ranked secondary endpoints and (2) additional, non-ranked endpoints.

Ranked secondary efficacy variables (ranked hierarchically in decreasing order) for the Maintenance Study are:

1. Proportion of Week 8 responders (per Full Mayo score) achieving endoscopic improvement (endoscopic subscore of 0 or 1) at Week 52.
2. Proportion of Week 8 responders (per Full Mayo score) taking steroids at Baseline who are steroid-free for at least 90 days at Week 52.

3. Proportion of Week 8 responders (per Full Mayo score) taking steroids at Baseline who are steroid-free for at least 90 days and in clinical remission (per Full Mayo score) at Week 52.
4. Proportion of Week 8 remitters (per Full Mayo score) achieving clinical remission (per Full Mayo score) at Week 52.
5. Proportion of Week 8 remitters (per Full Mayo score) achieving endoscopic improvement (endoscopic subscore of 0 or 1) at Week 52.
6. Proportion of Week 8 remitters (per Full Mayo score) taking steroids at Baseline who are steroid-free for at least 90 days at Week 52.
7. Proportion of Week 8 remitters (per Full Mayo score) taking steroids at Baseline who are steroid-free for at least 90 days and in clinical remission (per Full Mayo score) at Week 52.
8. Proportion of Week 8 responders (per Full Mayo score) with IBDQ response (increase of IBDQ ≥ 16 from Baseline) at Week 52.
9. Proportion of Week 8 non-responders (per Full Mayo score) with clinical remission (per Full Mayo score) at Week 52.
10. Proportion of Week 8 non-remitters (per Full Mayo score) with clinical remission (per Full Mayo score) at Week 52.
11. Proportion of Week 8 responders (per Full Mayo score) achieving endoscopic subscore of 0 at Week 52.
12. Proportion of Week 8 remitters (per Full Mayo score) achieving endoscopic subscore of 0 at Week 52.
13. Proportion of Week 8 responders (per Full Mayo score) with response in IBDQ Bowel Symptom domain (increase of IBDQ bowel symptom domain score ≥ 6 from Baseline) at Week 52.
14. Proportion of Week 8 responders (per Full Mayo score) with response in IBDQ fatigue item (increase of IBDQ fatigue item score ≥ 1 from Baseline) at Week 52.

As all these endpoints are categorical variables, NRI method of imputation, as described for the primary efficacy analysis, will be used for the missing values.

For the Maintenance Study endpoints, the difference between the adalimumab 40 mg eow treatment group versus the adalimumab 40 mg ew treatment will be assessed. The secondary endpoints at Week 52 that are of the categorical type will be analyzed using a two-sided CMH test adjusted for induction treatment regimen, and responder/remitter status at Week 8. Additionally, the CMH based two-sided 95% confidence interval (CI) for the difference in the proportions between the treatment groups will be calculated.

10.4 Additional Efficacy Analyses

Additional pre-specified endpoints in the Maintenance Study are as follows:

- Proportion of Week 8 responders (per Full Mayo score) with clinical response at Week 52.
- Proportion of Week 8 non-responders (per Full Mayo score) with clinical response at Week 52.
- Proportion of Week 8 non-responders (per Full Mayo score) with endoscopic improvement at Week 52.
- All cause and UC-related hospitalization and surgery rates during Weeks 8 – 52.
- Proportion of Week 8 responders per Adapted Mayo score (defined as decrease from Baseline in the Adapted Mayo Score ≥ 2 points and $\geq 30\%$ from baseline, PLUS a decrease in rectal bleeding subscore (RBS) ≥ 1 or an absolute RBS ≤ 1) achieving clinical remission per Adapted Mayo scores at Week 52.
- Proportion of Week 8 responders (per Full Mayo score) achieving Full Mayo Score, excluding the PGA subscore, ≤ 2 with no subscore > 1 at Week 52.
- Relationship between histologic scores and endoscopic improvement (endoscopy subscore of 0 or 1) at Week 52.
- Relationship between histologic scores and endoscopic subscore of 0 at Week 52.

- Proportion of Week 8 responders (per Full Mayo score) taking steroids at Baseline who are steroid-free for at least 180 days and in clinical remission (per Full Mayo score) at Week 52.
- Proportion of subjects who are taking corticosteroids at Baseline and are steroid free over time.
- Proportion of subjects achieving clinical remission per Partial Mayo (defined as a Partial Mayo score ≤ 2 with no subscore > 1) score over time.
- Proportion of subjects achieving clinical response per Partial Mayo score (defined as a decrease in Partial Mayo score of ≥ 2 points and $\geq 30\%$ from Baseline Plus a decrease in the rectal bleeding subscore [RBS] ≥ 1 or an absolute RBS of 0 or 1) over time.
- Change from Baseline in hs-CRP over time.
- Change from Baseline in corticosteroid dose over time.
- Change from Baseline in IBDQ score over time.
- Proportion of subjects with IBDQ total score ≥ 170 over time.
- Change from Baseline in Mayo score, Partial Mayo score and Mayo subscores over time.
- Change from Baseline in laboratory and nutritional parameters (e.g., hemoglobin, hematocrit, albumin, total protein concentration, and weight).
- Change from Baseline in subject-reported stool frequency (absolute values).
- Change from Baseline in work productivity and impairment questionnaire (WPAI) scores.
- Change from Baseline in SF-36 score.
- Change from Baseline in fecal calprotectin over time.
- Proportion of subjects with fecal calprotectin below 150 mg/kg over time.
- Time to achievement of remission (per Partial Mayo score).
- Time to achievement of response (per Partial Mayo score).
- Time to loss of response and factors associated with loss of response.
- Change in presence of extraintestinal manifestations.

The difference in proportions of subjects between treatment groups will be analyzed similarly as the ranked secondary endpoints and the CMH based two-sided 95% confidence interval (CI) for the difference in the proportions between the treatment groups will be calculated.

The difference in change from baseline between treatment groups will be analyzed using an ANCOVA model including factors of treatment, stratification variables and Baseline values. Parameter estimates with 95% confidence interval and *P* value will be provided.

NRI for missing data will be used for categorical endpoints. Mixed-Effect Model Repeated Measure (MMRM) model will be applied as the main analysis for the continuous endpoints.

Events of hospitalization and surgery will be identified by blinded adjudication of the serious adverse events (SAEs). Subjects in the integrated safety and Japan safety analysis sets for the Maintenance Study will be included in the all-cause and UC-related hospitalization and surgery rates analyses during the Maintenance Study.

All-cause hospitalization is defined as SAEs resulting in admission to the hospital or prolongation of an existing hospitalization for any reason. UC-related hospitalizations are defined as hospital admissions or prolongation of an existing hospitalization due to AEs or complications that are related to UC and included the following categories: UC-related surgery, hospitalizations for nonsurgical UC-related events, such as UC-related flares, and hospitalizations related to the complications/extra-intestinal manifestations of UC.

For all-cause and UC-related hospitalization and surgery rates during Weeks 8 – 52, adjusted incidence rates will be used to compare the risk between the treatment groups. Adjusted rates will be calculated as the number of subjects with the respective event divided by the time at risk. For subjects with an event during the study period, time at risk is the patient-years (PYs) from Week 8 to the first event. For subjects without an event during the study period, time at risk is PYs from Week 8 to the end of study follow up period. Relative risk ratios of the incidence rates and confidence intervals will be

calculated to evaluate the statistical significance of the difference between treatment groups using z-score normal approximations. Additionally, because subjects could have more than one hospitalization during the follow-up period, an event-based approach will be taken. The total number of hospitalizations during the Weeks 8 – 52 will be compared between the treatment groups using Poisson regression with the length of follow-up as the offset variable. Multiple events will be counted in this model.

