10.5 Handling of Multiplicity

The overall type I error rate of the primary and the ranked secondary endpoints will be strongly controlled using the approach of fixed-sequence multiple testing procedure.¹ Specifically, the testing will utilize the endpoint sequence of the primary and ranked secondary endpoints in the order as specified in Section 10.2 and Section 10.3 at the pre-specified alpha level. That is, only if success has been demonstrated for the primary endpoint of clinical remission will the testing continue to the first ranked secondary endpoint of endoscopic improvement. If success has been demonstrated for the first ranked secondary endpoint, then testing will continue to the next ranked secondary endpoint. Similarly, testing will continue through the other ranked secondary endpoints only if success was met for the preceding endpoint; otherwise, statistical testing will stop.

No multiplicity adjustment will be applied to the additional efficacy endpoints listed in Section 10.4. The analysis for additional efficacy endpoints will be performed at the nominal α level of 0.05 (two-sided).

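### The Poisson comparison of total hospitalizations counts repeat events per subject but states no allowance for overdispersion, so its intervals are too narrow if events cluster within subjects

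*SAP*

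**What the plan says.** Section 10.4 of the maintenance SAP plans two comparisons between treatment groups over Weeks 8 to 52.

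- **First-event rates**, for all-cause and UC-related hospitalization and surgery. Subjects with an event are divided by time at risk, which stops at the first event. Rate ratios and intervals are obtained "using z-score normal approximations".
- **Total hospitalizations.** The stated reason is that "because subjects could have more than one hospitalization during the follow-up period, an event-based approach will be taken". The totals are then compared "using Poisson regression with the length of follow-up as the offset variable. Multiple events will be counted in this model".

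The same section defines an all-cause hospitalization as an SAE leading to "admission to the hospital or prolongation of an existing hospitalization for any reason". On the analysis sets it says: "Subjects in the integrated safety and Japan safety analysis sets for the Maintenance Study will be included". Section 10.5 places the endpoints of Section 10.4 outside the fixed-sequence procedure, without multiplicity adjustment: "The analysis for additional efficacy endpoints will be performed at the nominal α level of 0.05 (two-sided"). Neither the maintenance SAP nor the induction SAP states a dispersion parameter, robust variance, random effect or negative binomial model for these counts.

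**The concern.** A Poisson model takes the variance of each subject's count to equal its mean. The offset corrects for unequal follow-up. It does not correct for subjects who are more prone to admission than others, or for one event making another more likely. The plan adds this analysis because it expects repeat admissions, which is the setting where the assumption is least secure. The event definition adds a second route: one illness may produce both an admission and a counted prolongation.

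Both routes push the same way. The model-based standard error is too small, the interval too narrow and the p-value too low. A programmer following the text as written would use the default unscaled standard errors. The comparison of total hospitalizations between ew and eow could then look firmer than the data allow.

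**Working it through.** **Inputs from the documents**
- Nominal two-sided level 0.05 (maintenance SAP, Section 10.5).
- Main Study 840 subjects, maintenance ratio 2:2:1 (induction SAP, Section 4.2): 840 × 2/5 = 336 each to eow and ew.
- Japan 100 subjects, ratio 1:1 (maintenance SAP, Section 4.2): 50 per arm.
- Integrated set: 336 + 50 = 386 per arm if every enrolled subject is re-randomized.
- Maintenance period 44 weeks, so mean count per subject μ = annual rate × 44/52.

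**Assumed, because the documents give no figure:** μ of 0.10 to 0.15 hospitalizations per subject, and gamma-distributed subject risk (frailty) with variance k.

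**Formulas.** With Y1 and Y2 events in the two arms, the model standard error of the log rate ratio is √(1/Y1 + 1/Y2). Under frailty, variance/mean is φ = 1 + kμ. The true standard error is √φ times the model one, and the actual level is α = 2[1 − Φ(1.96/√φ)].

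**Plan's own figure.** With k = 0, φ = 1 and α = 0.05. Simulation without clustering in the integrated set gave 0.045 to 0.047, so the nominal level is reproduced.

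**With clustering.** Mean admissions per hospitalized subject, μ/[1 − (1 + kμ)^(−1/k)], shows what each k implies.

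| k | φ (μ = 0.10; 0.15) | √φ | α, closed form | α, simulated | Admissions per hospitalized subject |
|---|---|---|---|---|---|
| 2 | 1.20; 1.30 | 1.10; 1.14 | 7.4%; 8.6% | 6.9-8.3% | 1.15; 1.22 |
| 5 | 1.50; 1.75 | 1.22; 1.32 | 11%; 14% | 10-14% | 1.28; 1.42 |
| 10 | 2.00; 2.50 | 1.41; 1.58 | 17%; 22% | 16-21% | 1.49; 1.71 |

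With k = 1 the closed form gives 6.2% and 6.8%. A separate simulation at 0.1 and 0.2 per patient-year (μ = 0.085 and 0.169) gave 5.7% and 7.0%. In the closed form φ depends on rate and clustering, not on sample size, so the 386 is not critical.

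**Prolongations.** Suppose 20% of admissions also yield one counted prolongation and there is no frailty. Then φ = (0.8 × 1² + 0.2 × 2²)/(0.8 × 1 + 0.2 × 2) = 1.6/1.2 = 1.33, and α is about 9%. Simulation gave 8.6% to 8.8%.

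**Japan set, 50 per arm, full follow-up, simulated.** At 0.1 per patient-year (about 8 events in all) the unscaled test stays between 1.4% and 4.8% for k up to 8, because events are too few for the Wald test to reach its level. At 0.4 per patient-year it runs at 8% to 30% for k = 1 to 8.

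**Remedies, simulated with full follow-up**
- Integrated set, k = 1 to 8, rates 0.1 to 0.4 per patient-year: subject-level sandwich variance 4.7% to 6.1%; Pearson-scaled 4.5% to 5.5%. The unscaled Poisson test gave 5.7% to 31.1% over the same grid.
- Japan set: the sandwich reached 8.8% (k = 8, 0.4 per patient-year). The Pearson-scaled test did not exceed 5% there, or 5.6% when about 30% dropout was added. At 0.1 per patient-year it is conservative, near 1%.
- Negative binomial regression was not simulated. The case for it is that its variance has the form μ(1 + kμ) used above.

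**Empty arms in Japan.** The chance that at least one arm has no event is 1 − (1 − e^(−50r))² for r events per subject: 1.3% at r = 0.10, 0.1% at 0.15, 16% at 0.05, 40% at 0.03 and 85% at 0.01.

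**The case against.** The best case for leaving the text alone has four parts.

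- **The size is assumed.** No event rate or dispersion appears in the documents. With mild clustering the level is 6-7%, which matters little for one of many unadjusted endpoints. This stands: the direction is firm, the size conditional. The 16-21% figures need variance 10, or about 1.5 to 1.7 admissions per hospitalized subject within 44 weeks, and should not be read as the expected outcome.
- **A sound analysis is already there.** The first-event comparison counts each subject once, so within-subject clustering does not touch it. This also stands, but it does not repair the second analysis, which is reported with its own interval.
- **Nothing confirmatory depends on it.** True. Still, lack of multiplicity control does not excuse a single test from meeting its own nominal level.
- **The plan does not rule out a correction.** It is silent on the point. But a plan written to guide programming, which names the model and the offset and nothing more, will be read as unscaled Poisson.

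A reader might also infer that the z-based rate ratio will probably fail in Japan because an arm has no event. The documents do not support that for hospitalization. At the rates assumed above the chance is 1.3% or less, and 0.3% to 6% even with frailty variances of 2 to 10. It passes one half only at rates well below 0.03 per subject. Surgery may be that rare, but no figure is given.

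**Conclusion.** The point holds as a limited one. As written, the event-based comparison gives standard errors that are too small whenever subjects differ in risk or an admission and its prolongation both count. In the integrated set, at an assumed 0.10 to 0.15 events per subject, the nominal 5% test runs at about 7-9% with frailty variance 2 and 10-14% with variance 5. The true standard error is 1.10 to 1.32 times the model's. With mild clustering, or with sparse events in the Japan set, the test is near or below its nominal level.

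The consequence is confined to one additional, non-ranked analysis. The documents do not support extending it to the first-event rates, to the primary or ranked secondary endpoints, or to the trial's main conclusions.

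**What to change.** Amend the total-hospitalization analysis in Section 10.4 of the maintenance SAP before it is run:

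- **Integrated safety set:** negative binomial regression with log follow-up as offset, or Poisson with the same offset and a subject-level robust or Pearson-scaled variance. Name one as the analysis.
- **Japan safety set:** Poisson with a Pearson-scaled standard error, because the sandwich variance can run high at 50 per arm.
- **Event count:** state whether a prolongation of an existing stay counts as a separate hospitalization.
- **Minor:** where an arm has few or no events, use an exact conditional or mid-P interval for the first-event rate ratio in place of the z approximation. If both arms have none, report counts only.

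The cost is a few sentences and a changed procedure option, with no new data. Intervals become somewhat wider, and in the Japan set the scaled test is conservative when events are very few.
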